2.6 Overview and Rationale of Study Design

The SHARP study is a single-center open-label, Phase 2 clinical trial of stereotactic body radiation therapy (SBRT), hormone/androgen deprivation therapy (ADT) and radium Ra 223 dichloride for participants with newly diagnosed oligometastatic castration sensitive prostate cancer.

Eligibility

Participants will be adults diagnosed with metastatic prostate adenocarcinoma who have undergone full treatment at the primary prostate site. Participants will be chemotherapy naïve to metastatic sites, unless exposure occurred during treatment for primary disease.

Oligometastatic burden will be limited to a maximum of four lesions, consistent with a summary analysis demonstrating improved prognosis for SBRT in prostate cancer for participants with four or fewer lesions [22]. In addition, participants must have at least one bone lesion to increase benefit over any risk from the bone specific radium Ra 223 dichloride regimen.

Participants must have at least one bone lesion and each non-visceral lesion (bone and lymph node) should not exceed more than 5 cm. In addition, participants may have one lung lesion (< 2cm); no liver lesions are permitted.

Treatment program

The treatment program is comprised of SBRT, administered over the first cycle, radium Ra 223 dichloride administered over 6 cycles, and concurrent standard of care ADT (luteinizing hormone-releasing hormone agonist-either leuprolide or goserelin, or LHRH antagonist degarelix or relugolix). Each treatment cycle is 28 days.

Participants will be receiving ADT for approximately 36 weeks as part of this study (can be started prior to consent) to increase radiosensitivity [23, 41]. Metastatic prostate cancer patients often present at COH having initiated standard of care ADT. Therefore, there is no benefit derived from monitoring patients during their initial single-agent standard of care ADT.

Typically standard of care ADT is continued indefinitely however it is associated with side effects of fatigue, hot flushes, erectile dysfunction, muscle loss, osteoporosis and sometime “drug holidays” are given. Thus, ADT will be discontinued after a total of 36 weeks and participants will be monitored carefully. We hypothesize that some patients may achieve long-term remission off ADT, however upon disease recurrence ADT (and other appropriate standard treatment) will be resumed.

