Patients with asymptomatic low volume locoregional recurrent disease will be allowed to enroll on this study after discussion with the PI. In the case where the low volume recurrence is amenable to SBRT, it will be included in the SBRT treatment. In the case where the low volume recurrence is not amenable to SBRT based on reirradiation risk, then we will follow these lesions with re-imaging scans and reassess at later time points for further local control, which will be allowed on study. Additionally, if these patients fail only at the untreated site (due to the untreated recurrence/disease not being amenable to SBRT) they will be censored in the primary efficacy analysis at that time. Patients with high risk disease in which salvage radiation to the prostate bed is recommended in the absence of lesions noted on scans will be allowed to enroll after discussion with the PI. In these cases, salvage radiation to the prostate bed may occur at the same time as the SBRT.

Radium Ra 223 dichloride will be administered during ADT therapy based on the knowledge of general synergy between ADT and radiation therapies in the treatment of prostate cancer. Radium Ra 223 dichloride has been developed as a treatment given concurrently with ADT therefore safety of that combination has been established. The purpose of radium Ra 223 dichloride therapy is to enhance anticancer effect against known oligo bone metastases required for eligibility for this study, but also treatment of likely invisible bone micrometastases. Laboratory tests will be monitored every 4 weeks and general guidelines for administration of Radium 223 will be followed. These include: for the 1st dose of Radium 223 baseline laboratory test need to be: Hgb \geq 9.0 g/dL, ANC \geq 1,500 cells/mm³, platelets \geq 100,000 cells/mm³. For subsequent infusions (2-6) there is no Hgb requirement, ANC \geq 1,000 cells/mm³, platelets \geq 50,000 cells/mm³.

Up to 7 cycles of protocol therapy are planned in the absence of unacceptable toxicity or disease progression, whichever comes first. If one agent is discontinued due to toxicity, then the participant may continue to receive the other protocol therapy agent(s).

In addition to capturing efficacy endpoints, participants will undergo follow-up up to 5 years to capture long term toxicities (e.g. secondary malignancies) due SBRT and/or radium Ra 223 dichloride.

Efficacy

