Prostate-specific antigen (PSA) assessments will occur every cycle during protocol therapy and then every 3 months during Response Follow-up to mimic the ongoing STOM trial [24]. Tumor evaluation will occur pre-SBRT and then at the post Ra-223 visit (post-6 doses of radium Ra 223 dichloride), and during Response Follow-up (every 6 months and at PSA progression).

This study will assess response via PSA levels alone and also use combined PSA and tumor evaluations per the modified Prostate Cancer Working Group 2 criteria [43]. Time to treatment failure will be a primary efficacy endpoint.

Correlative Tumor Studies

Genomic alterations in prostate cancer are being extensively studied although majority of data pertains to metastatic castration resistant prostate cancers (mCRPC) and primary tumors, with relative scarcity of information regarding metastatic hormone sensitive sites. Approximately 90% of mCRPC patients harbor

clinically actionable molecular alterations. Alterations in androgen receptor (AR) signaling pathways, ETS genes, TP53, and PTEN are reported in about 40-60% of patients. Other genomic alterations include *PIK3CA/B*, *RSPO*, *RAF*, *APC*, β -catenin, and *ZBTB16*. Germline and somatic alterations in DNA repair genes gathered significant attention because of potential implications for sensitivity to PARP inhibitors and platin chemotherapy. 23% of mCRPC patients harbor DNA repair pathway aberrations (BRCA2, BRCA1, ATM) and 8% harbor germline findings [44]. Exploratory biomarker analysis on baseline pre-SBRT archival and fresh tissue will be performed. A prostate cancer biomarker panel (e.g. Foundation One platform) will be utilized to analyze genomic alterations in metastatic prostate cancer prior to development of castration resistance.

Correlative Blood Studies

The purpose of the blood correlatives of the study is to assess *in-vivo* effects of radiation on expression of proteins related immune suppression in patients with metastatic prostate cancer. Circulating immune cell populations and plasma levels of cytokines, chemokines and growth factors will be assessed. From this data, we will be able to determine the feasibility of conducting future first-in-human studies involving pathway-specific and novel immunotherapeutic agents for this disease site.

Alkaline Phosphatase Normalization Studies

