5.7 Follow-Up

After End of Treatment assessments, all participants will enter follow-up for a maximum of 5 years. This is comprised of:

- **Response Follow-up-** for those who have yet progress
- **Long-term Follow-up-** for all participants who have progressed OR completed Response Follow-Up for survival and long-term toxicities. This follow-up will be performed typically via medical record review.

Assessment time points and windows are detailed in [Section 11.0](#).

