- e. *Cycle 1 Day 1*: With the exception of PSA, serum testosterone and blood counts other screening evaluations performed within 14 days prior to Cycle 1 Day 1 of protocol therapy may serve as Day 1 baseline evaluations.
- f. Participants must meet criteria in [Section 6.1](#) to initiate SBRT on Cycle 1 Day 1.
- g. Assessments must be performed **within 7 days** prior to radium Ra 223 dichloride. Safety assessments must be reviewed within 7 days prior to initiating a new cycle.
- h. *Cycle 2 Day 1 (1st dose of radium Ra 223 dichloride)*: Participants must meet criteria in [Section 6.2](#).
- i. *Post Ra-223/EOT visit to occur approx. 28 days +/- 7 days post-last dose of Ra 223 dichloride*.
- j. *Response follow-up* assessments for participants yet to progress, will occur ~ every 3 months (± 4 wks) (except [tumor evaluations](#)) from the day of last response evaluation until progression or the initiation of a new therapy.
- k. *Long-term follow-up* assessments for participants who progressed or ended Response Follow-up to occur annually (± 30 days) or as requested by the Study PI via medical record review, review of social security registry/ public records, and/or telephone call.
- l. *Informed consent* process to be fully documented (see [Section 17.4](#)). Informed consent must occur prior to any research only (non-SOC) screening procedures.
- m. *Medical history* to include a review of treatment history, any ongoing medical conditions and medical history pertaining to eligibility on study and involvement during study.
- n. *Eligibility criteria* are detailed in [Section 3.0](#).
- o. *Registration* into a COH clinical trial management system (CTMS).
- p. *Standard physical exam* includes weight and skin analysis.
- q. *Vital signs*: heart rate, blood pressure, respiration rate, and temperature.
- r. *Concurrent medications* and reason for administration to be documented in the EHR and eCRF from within 56 days prior to protocol therapy up to EOT visit. See [Section 5.11.1](#) for concomitant medication restrictions and guidelines.
- s. *Adverse event (AE)* will be assessed using CTCAE v.5.0.
- t. Active AE reporting will start from start of treatment until the post RA-223 visit/EOT visit **NOTE**: The highest AE grade per cycle will be reported in the eCRF from start of therapy until the EOT visit. **Exceptions to expedited reporting** are stated in [Section 8.2](#)

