- u. Long-term toxicities -- secondary malignancy, thyroid dysfunction-- attributed to protocol therapy will be collected via medical record review and/or phone call during Response Follow-up, standard of care visits and Long-term Follow-up. **NOTE**: If the participant is no longer at COH, the study team will request relevant medical information from the external institution.
- v. If clinically indicated by history of cardiovascular disease.
- w. *Serum chemistry* panel to include: glucose, Blood Urea Nitrogen (BUN), creatinine, total protein, albumin, magnesium, bicarbonate, calcium, sodium, potassium, chloride, total bilirubin, alkaline phosphatase, ALT and AST.
- x. *Immune biomarker studies*: Collect 20 mL per timepoint in sodium heparin green-top tubes and store on ice until delivery to [name] laboratory (See [Section 10.2](#) for details). **NOTE**: Notification to the [name]'s laboratory of pending sample collection must be made **at least 1 day in advance** (see [Section 10.2.1](#) for details).
- y. *Tumor tissue*: If available, archival metastatic or primary tissue will be submitted for clinical testing. Refer to [Section 10.1](#) for additional details.

- z. *Fresh metastatic tissue (optional)*: If the participant is willing attempts should be made to take extra metastatic tissue for clinical testing at the time of standard of care biopsy. See also [Section 10.1](#).
- aa. *Tumor Evaluation*: Options include combination of: CT chest, abdomen, pelvis, CXR, targeted X-rays, bone scan, Whole Body MRI, MRI of the TLS spine, MRI of the pelvis, PET/CT. All anatomical areas of the body need to be included (chest, abdomen, pelvis, skeleton) using combination of these tests. Follow up scans should at the minimum include the same scans utilized for screening.
- bb. Tumor evaluation to occur every 6 months (\pm 14 days) from last tumor evaluation, and at PSA progression (unless taken within the last 4 weeks).
- cc. Refer to [Section 5.3](#) for the treatment plan. Refer to [Section 6.3](#) for dose modification/ delay guidelines and [Section 5.9](#) for supportive care guidelines.

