12.0 ENDPOINT EVALUATION CRITERIA/MEASUREMENT OF EFFECT

12.1 Efficacy Endpoints

Response and progression will be evaluated in this study using modified Prostate Cancer Working Group 2 criteria [43] (see [Appendix C](#) and [Appendix D](#)). PSA levels will be a part of overall response assessment. Other clinical efficacy endpoints are described in [Table 12.1](#).

Table 12.1 Efficacy Endpoints

Endpoint	Definition
Time to treatment failure (TTF)	Time from the initiation of ADT for metastatic disease until PSA increase to > pre-ADT level or PSA >10 (whichever is smaller) or radiographic or clinical progression or resumption of ADT by physician's choice
Objective response rate (ORR)	Proportion of patients achieving CR or PR at Cycle 8 Day 1 (post-6 doses of radium Ra 223 dichloride)
Complete response (CR) rate	Proportion of patients achieving CR
Progression-free survival (PFS)	Time from the initiation of ADT for metastatic disease until PSA progression or radiographic progression or death
Bone specific progression-free survival (Bs-PFS)	Time to progression of bone specific disease over baseline
Duration of response (DOR)	Time from documented response to recurrent or progressive disease is first met
Duration of overall complete response	Time from documented CR to recurrent/ progressive disease
Duration of stable disease	Time from start of treatment until the criteria for progression are met, taking as reference the smallest measurements recorded since the treatment started.
Overall Survival (OS)	Date of initiation of protocol treatment to date of death from any cause

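### After a first failure by PSA or outside bone, or after a new therapy, the plan requires no further collection of bone status, and bone-specific PFS has no rule for these patients or for death

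*Combined protocol and SAP*

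**What the plan says.** - **Endpoint.** Bone-specific PFS is a secondary objective (Section 1.2). Table 12.1 defines it only as "Time to progression of bone specific disease over baseline". It gives no start date, no death component and no censoring rule. Section 13.5 lists it among the secondary analyses without a method.
- **End of scheduled imaging.** Table 11.0 marks tumor evaluation at Screening, Post Ra-223/EOT and Response Follow-up. Footnote j runs Response Follow-up "from the day of last response evaluation until progression or the initiation of a new therapy".
- **What follows.** Section 5.7 describes Long-term Follow-up as being "for all participants who have progressed OR completed Response Follow-Up for survival and long-term toxicities". Its column in Table 11.0 holds only AE assessment and survival. Footnote k has it done annually from records or by telephone.
- **What counts as progression.** Footnote j does not name a type. PFS in Table 12.1 counts PSA progression, and the overall response table in Appendix D makes a PSA rise alone progressive disease whatever the lesions show.
- **Scan at PSA failure.** Footnote bb requires a tumor evaluation at PSA progression unless one was done in the preceding 4 weeks. Footnote aa says of tumor evaluations: "All anatomical areas of the body need to be included (chest, abdomen, pelvis, skeleton) using combination of these tests".
- **Therapy after failure.** Section 2.6 states that "upon disease recurrence ADT (and other appropriate standard treatment) will be resumed".
- **Role of radium.** Section 2.6 also states: "The purpose of radium Ra 223 dichloride therapy is to enhance anticancer effect against known oligo bone metastases", and adds presumed bone micrometastases as a target.

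**The concern.** Of the listed efficacy endpoints, bone-specific PFS is closest to what radium is meant to do. The follow-up rule was written around first progression of any type, and this endpoint needs observation beyond that. A patient who fails first by PSA, or radiographically outside bone, leaves scheduled imaging while still at risk of bone progression, and probably at higher risk than before.

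With no stated rule, the default would probably be a Kaplan-Meier curve censored at the last scan. That censoring is likely to be informative, and it would make bone control look better than it was. In a single-arm trial there is no control group to expose the distortion, so a favourable curve could be read as a bone benefit of radium.

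**Working it through.** The plan gives no figure for bone-specific PFS. Its one quantitative design claim, power above 80% for TTF (24 patients, 16 months of accrual, 18 of follow-up, median 16 against 32 months, one-sided 10%), reproduces at 0.83 to 0.89 under an exponential model. It is used here only as a source of inputs.

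**1. What is observed, by route of first failure**

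| First failure | Bone status at failure | Bone status afterwards |
|---|---|---|
| Bone progression on a scan | Event observed | Not needed |
| PSA progression | Observed (footnotes aa, bb) | No collection required |
| Radiographic, outside bone | Observed on that scan | No collection required |
| New therapy before progression | Last scheduled scan only | No collection required |

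**2. How many patients**

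Inputs from Section 13.5: n = 24, accrual A = 16, follow-up F = 18, medians 16 and 32 months, and the 25-month critical value as a middle case. Assumptions: exponential time to first failure of any kind; a share s of first failures, from 20% to 80%, shows bone progression, including on the PSA-triggered scan. The documents give no such share.

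P(failure by cutoff) = 1 − [exp(−λF) − exp(−λ(F+A))]/(λA), with λ = ln 2/median. Patients affected = 24 × P × (1 − s).

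For median 16: λ = 0.0433, P = 1 − (0.4585 − 0.2293)/0.693 = 0.669, so 24 × 0.669 = 16.1 failures.

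| Median (months) | Failures at cutoff | Affected, s = 80% to 20% | Failures by 60 months | Affected, s = 80% to 20% |
|---|---|---|---|---|
| 16 | 16.1 | 3.2 to 12.8 | 22.2 | 4.4 to 17.8 |
| 25 | 12.2 | 2.4 to 9.8 | 19.5 | 3.9 to 15.6 |
| 32 | 10.3 | 2.1 to 8.2 | 17.5 | 3.5 to 14.0 |

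This gives about 2 to 13 patients at the cutoff and 4 to 18 by 60 months. Section 13.3 now expects 66 months of accrual. With 18 months of follow-up after that, failures are 20.4 (median 16) and 15.4 (median 32), so 0.2 × 15.4 = 3 to 0.8 × 20.4 = 16 are affected.

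**3. Bias if these patients are censored at first failure**

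Let a be the hazard of non-bone failure, b the bone hazard before it and c the bone hazard after it; deaths are ignored.

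- True bone-progression-free proportion: S(T) = exp(−(a+b)T) + [a/(a+b−c)] × [exp(−cT) − exp(−(a+b)T)].
- Censored Kaplan-Meier curve: exp(−bT), whatever c is.

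*Model 1:* assumed median 25 months to any failure, 30% of failures in bone. Then a + b = 0.02773, b = 0.00832, a = 0.01941. At 36 months Kaplan-Meier reads exp(−0.2994) = 74.1%. For c = 2b = 0.01664, the true value is 0.3686 + 1.75 × (0.5494 − 0.3686) = 68.5%.

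| c/b | True, 36 months | Gap from 74.1% | True, 60 months (Kaplan-Meier 60.7%) |
|---|---|---|---|
| 1 | 74.1% | 0 | 60.7% |
| 2 | 68.5% | 5.6 points | 50.3% |
| 3 | 63.9% | 10.2 points | 43.0% |
| 5 | 57.1% | 17.0 points | 33.9% |

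With 50% of failures in bone, Kaplan-Meier reads 60.7% at 36 months against 55.3%, 51.4% and 46.4%: gaps of 5.4, 9.3 and 14.3 points.

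*Model 2:* assumed non-bone failure median 20 months and bone median 80 months before failure, so bone is first in 20%. At 24 months Kaplan-Meier reads 81.2%.

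| Post-failure bone median (months) | Fold rise | True, 24 months | Gap |
|---|---|---|---|
| 12 | 6.7 | 60.2% | 21.0 points |
| 18 | 4.4 | 66.5% | 14.7 points |
| 30 | 2.7 | 73.2% | 8.0 points |
| 80 | 1 | 81.2% | 0 |

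**The case against.** **A reader might infer that bone-specific PFS cannot be observed at all in patients who fail first by PSA or outside bone.** The documents do not support that. Footnotes aa and bb require a scan covering the skeleton at PSA progression. PSA progression is set against the pre-ADT baseline (at least 25% above it and over 2 ng/mL, Appendix C), so that scan does not come at an early biochemical rise. Only bone progression after it is lost.

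**Other text softens the gap.** Section 9.3.2 has local control judged on later standard-of-care imaging including bone scan. Sections 2.6 and 5.9.1 provide re-imaging for untreated locoregional recurrences. Footnote k lets the study PI request long-term assessments. None of these requires bone progression to be recorded after first failure. The Appendix D line urging documentation of objective progression concerns symptomatic deterioration and carries no schedule.

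**A reader might also infer that all such patients will be censored, or that PFS has the same defect when ADT is resumed early.** No censoring rule for bone-specific PFS is stated, so censoring is a probable default and not a fact. The PFS inference needs resumed ADT to count as a new therapy. ADT is a protocol component and the documents do not classify its resumption.

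**The size depends on assumptions.** Large gaps need a large rise in bone hazard, and no document supports a particular rise. Therapy resumes at recurrence, which may restrain it; Section 2.2 gives 14 to 30 months as median time to progression of any kind on androgen suppression. Nor would 12 to 19 of 24 patients (50% to 80%) be affected at the cutoff, since that assumes every patient has failed.

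**Stopping at a new therapy is a recognised choice of estimand.** This stands in part. Bone status after failure mixes in later treatments, and unscheduled imaging is itself informative. It is a reason to report both analyses, and does not excuse leaving the rule unstated.

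**Conclusion.** The gap is real but narrower than a quick reading suggests. Bone progression present at first failure is captured; bone progression after the PSA-triggered scan, after a non-bone radiographic failure or after a new therapy is not systematically collected. The endpoint has no rule for these patients or for death. Reading footnote j's progression as including PSA alone is an inference, well supported by the PFS definition and Appendix D.

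Any Kaplan-Meier bias would probably be upward, but its size is uncertain: zero with an unchanged bone hazard, about 5 to 17 points at 36 months for a 2- to 5-fold rise, or 8 to 21 points at 24 months with a post-failure bone median of 12 to 30 months. These figures illustrate assumed exponential models and are not predictions. The count of 2 to 13 patients at the cutoff and 4 to 18 by 60 months rests on the assumed 20% to 80% bone share.

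The endpoint is secondary, with no hypothesis or decision rule, and the primary TTF analysis is not affected. The change is worth making because it is cheap.

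**What to change.** 1. **Section 5.7 and footnotes j and k.** State that after a PSA-only or non-bone progression, or a new therapy, the date and result of each later standard-of-care bone imaging study are abstracted at the annual Long-term record review, until first bone progression, death or 5 years. State also whether resumed ADT counts as a new therapy for footnote j.
2. **Table 12.1.** Give the endpoint a start date. Define it as first bone progression or death, without censoring at PSA or non-bone progression.
3. **Section 13.5.** Also report the cumulative incidence of bone progression with death as a competing event. Add a sensitivity analysis of bone as the first failure, with PSA or non-bone failure and new therapy as competing events. The two together cover both reasonable estimands.

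The cost is a footnote change and a case report form field at a review already planned, with no added scans and no change to treatment. The downside is that imaging after progression is irregular and reflects later therapies. The report should say so, and the result must not be read as an effect of radium alone.
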